We plan to examine the impact of low pressure during RALP with the intention of identifying whether lower pressures might benefit patients. We hypothesize that a low insufflation pressure may provide an improvement in postoperative pain and abdominal distension in addition to potential physiologic benefits, and that these factors might then allow a shorter hospital stay. We previously initiated a protocol in September of 2016 (IRB# 1066864) to perform RALPs at an insufflation pressure of 6 mmHg with the intention of increasing the pressure as needed on an individual patient level. In order to determine whether this might allow earlier discharge when successful, we began allowing for same-day discharge in patients meeting appropriate criteria. Having now demonstrated feasibility in over 300 consecutive patients using this ultralow pneumoperitoneum protocol, we now plan to conduct a randomized trial to compare a pressure of 6 mmHg with patients having RALP at a standard pressure of 15mmHg to determine whether there is a true benefit.

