	

ii. Wound infection (y/n)

c. Length of stay (days; typically 0 to 1)

i. Discharge date/time (m-d-y; hh:mm)

3. Use of postoperative pain medication

a. Opioids (y/n for each: fentanyl, Dilaudid, oxycodone, Norco, tramadol, Percocet, Demerol)

i. Morphine equivalents (MME)

b. Non-opioids (y/n for each: Toradol, Tylenol, oxybutynin)

4. Postoperative pain scores (0-10; asleep, missed, or discharged)

a. Average and maximum scores during each interval (during the PACU stay, the first 4 hours on the floor, next 8 hours, and the following 8 hours; as well as the final score immediately prior to discharge)

b. At each location (abdomen, legs, groin, scrotum, shoulder, other/specify)

5. Timing of ability to pass gas (day 0, day 1, day 2, >day 2)

6. Clinically-significant ileus (i.e., requiring treatment; y/n)

Follow-Up (1 week, 1 month, & 3 months)	

1. QoR-15 (0-150) – only asked at week 1

a. Collected (y/n)

b. Score (0-150)

2. Prescription(s) given (y/n) – only asked at week 1

a. Prescription(s) filled (y/n)

b. Opioids (y/n for each: fentanyl, Dilaudid, oxycodone, Norco, tramadol, Percocet)

i. Number of pills taken for each (#)

ii. Morphine equivalents (MME)

c. Non-opioids (y/n for each: Toradol, Tylenol, oxybutynin)

3. Scrotal swelling (y/n) – only asked at week 1

4. Leg weakness (y/n)

a. Left, right, bilateral

b. Degree of weakness (each leg; mild, moderate, severe)

c. Impaired ability to walk

d. Impaired ability to drive

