**Table 2. Post-operative pain monitoring schedule.**

Timeframe	Description	Time-Points	Pain Locations
During PACU stay	Upon admission to the PACU (typical stay of 1-2 hours)	PACU	Abdomen Legs
1 st 4 hours on the floor	Every 2 hours during the first 4 hours on the floor	Floor-0, 2, & 4 (hours 0 through 4)	Groin Scrotum
Next 8 hours on the floor	Every 2 hours during the next 8 hours on the floor	Floor-6, 8, 10, & 12 (hours 5 through 12)	Shoulder
Following 8 hours on the floor	Every 2 hours during the following 8 hours on the floor	Floor-14, 16, 18, & 20 (hours 13 through 20)	Other/specify
Final score immediately prior to discharge	Recorded on the floor prior to discharge; OR via phone call by CRC for those discharged same-day	Discharge, or Post-discharge	

1-Scores measured only while inpatient (or post-discharge for those discharged same-day) and awake; measures not taken in <1 hour from planned time will be marked as "missed."

Pain scores are measured using an 11-point numerical rating scale (NRS), in which a rating of 0 corresponds to no pain, 1-3 indicates mild pain, 4-6 indicates moderate pain, and 7-10 corresponds to severe pain. Scores are recorded by nursing staff as part of routine care in the PACU and on the postoperative recovery floor during the inpatient stay, however these measures are often not recorded in a consistent fashion with respect to timing. Therefore, we will record scores every 2 hours during the inpatient stay while the patient is awake (with the exception of the PACU, which occurs only at admission), and determine the average and maximum scores reported over sequential timeframes: during the PACU stay (typical stay of 1-2 hours), the first 4 hours on the floor, next 8 hours, and the following 8 hours; as well as the final score immediately prior to discharge (see Table 2). There will be no strict time window due to the variability of sleep schedules and discharge timing during the short inpatient stay, however, scores will be marked as "missed" if not recorded in <1 hour of the planned time. Pain will be measured with respect to the abdomen, legs, groin, scrotum, shoulder (due to insufflation), and "other" location. Pain medication morphine equivalents (MME) will also be measured over the same sequential timeframes during the inpatient stay through 1 week postoperatively. Patients

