will be educated on the importance of bringing all medications to follow-up visits, which will lead to more accurate pain medication counts and calculations.

Patients are typically discharged on Day 0-1, and for those discharged on Day 0 (i.e., same-day), the CRC will call the following morning to evaluate pain (see Appendix C). Because we are targeting same-day or next-day discharge, there is the potential for missing data in the first 24-hour period. Therefore, there will be no restrictions or protocol deviations for pain scores, as we are collecting scores only while inpatient/awake and via phone call for those discharged same-day. Follow-up visits per routine care occur at approximately 1 week postoperatively for catheter removal, as well as at 1 month and 3 months. Appointments will follow routine scheduling practices for the office, which may include variance in exact visit timing. Generally, patients will have 1 week postoperative visit around 5-7 days after surgery, but may be delayed further by approximately 1 week depending on scheduling availability and/or clinical indication (e.g. need for cystogram). Follow-up visits are generally 1 month and 3 months post-surgery, but may occur approximately a couple weeks before or after as per physician standard of care scheduling to accommodate patient and physician availability. There will be no strict visit windows to allow for visit scheduling flexibility. Because the majority of RALP patients will be eligible for participation, schedulers will be educated on the importance of return visit timing accuracy. There will be no extended or long-term follow-up via direct patient contact or EMR review.

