## 2.4 – Statistical Analysis

The demographic and clinical characteristics of male patients age 18 or older with prostate cancer who are eligible and electing to undergo robotic assisted laparoscopic prostatectomy (RALP) at OhioHealth Dublin Methodist Hospital (DMH) Robotic Urology with the Principal Investigator will be reported using means and standard deviations or medians and interquartile ranges for continuous variables, or frequencies and percentages for categorical variables. We plan to compare the clinical outcomes of patients between different insufflation pressures (6 versus 15 mmHg). Continuous variables will be compared between two groups using independent sample t-test or Mann-Whitney U test, as appropriate, and categorical variables will be compared using Chi-square test or Fisher's exact test, as appropriate.

During the previous feasibility study of RALPs at an insufflation pressure of 6 mmHg, we found that there was a significant difference in pain scores at 5-12 hours. The average score in the 6 mmHg group was 3.2, and that in 15 mmHg historical group was 3.9. Using these values and an assumed standard deviation within each group of 1.4 (effect size = 0.5), at a significance level of 0.05 to achieve 90% power, the estimated sample size will be 86 patients in each group (total 172 patients). However, to account for ineligible patients after enrollment (estimated 10%), we will enroll minimum of 192 patients.

**Aim #1) Compare average postoperative pain medication use between groups, as measured in total morphine equivalents (MME) over time at pre-specified time intervals through follow-up at 1 week.**

Postoperative medication use between the two groups will be assessed at the following time points: during the PACU stay, during the first 4 hours on the floor, next 8 hours, the following 8 hours, and following discharge through the 1-week follow-up visit. Both total and average medication use measured in total morphine equivalents at/during each time point will be calculated and compared between two groups (6 versus 15 mmHg) using independent sample t-test or Mann-Whitney U test, as appropriate.

**Aim #2) Compare average and maximum postoperative pain scores between groups, as measured using the self-reported 11-point numerical rating scale (NRS), over time at pre-specified time intervals through discharge.**

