**Aim #4) Compare average length of stay (typically 0-1 days) between groups.**

The average length of stay postoperatively will be compared between the two groups using independent sample t-test or Mann-Whitney U test, as appropriate. Also, the proportion of patients in each group who went home on day 1 versus day 0 will be compared using Chi-square test or Fisher's exact test, as appropriate. A difference of 10% in the proportion of patients will be considered clinically significant.

A p-value of less than 0.05 will be considered statistically significant for analysis. All of the analyses will be performed using SAS Enterprise Guide, version 7.1 (SAS Institute, Cary, NC).

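### Aim 1 compares opioid use only window by window, so the day of discharge decides where first-night use is counted; a supportive per-patient total and a stated rule for discharged patients are needed

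*Combined protocol and SAP*

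**What the plan says.** Section 2.4, Aim #1, lists five windows for MME: PACU, three floor windows of 4, 8 and 8 hours, and the time at home. The list closes with "the following 8 hours, and following discharge through the 1-week follow-up visit". The comparison is then set per window: "Both total and average medication use measured in total morphine equivalents at/during each time point will be calculated", by t-test or Mann-Whitney test.

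Section 2.3, in the text below Table 2, says that MME is "measured over the same sequential timeframes during the inpatient stay through 1 week postoperatively". For home use, Table 1 (Follow-Up) records "Number of pills taken for each" at week 1 and lists no dose times.

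Discharge is usually on day 0 or day 1 (Section 2.3). Section 1.1 hypothesises less pain and distension with low pressure, and that "these factors might then allow a shorter hospital stay". Aim #4 compares day-0 with day-1 discharge between arms and adds: "A difference of 10% in the proportion of patients will be considered clinically significant".

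Table 1 has a code for patients who have left, but only for pain: "Postoperative pain scores (0-10; asleep, missed, or discharged". No such code is listed for MME.

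**The concern.** The same opioid dose, taken on the same night, lands in a floor window if the patient stayed and in the home window if he left. Which of the two happens is a post-randomisation event that insufflation pressure may itself change. The later floor windows therefore compare either a subset selected by discharge or, if patients who have left are given 0 MME, a mixture of opioid use and discharge timing. In the second case, earlier discharge in the 6 mmHg arm could look like lower opioid use.

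A per-patient sum across windows would not depend on where the dose was taken, but the plan defines none. Home use is recorded without dose times, so first-night home doses cannot be put back into the hourly windows afterwards. The floor windows also stop at 4 + 8 + 8 = 20 hours, so MME between hour 20 and discharge belongs to no listed window.

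**Working it through.** **Is a per-patient total defined anywhere?** In Aim #1 the word total is tied to each time point, and total morphine equivalents names the unit. The Section 2.3 sentence gives the span of collection, not a summed endpoint. The regression described after Aim #2 refers to medication use without defining it. No sum across windows is defined.

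**The plan's own figure.** The only sample size is for the pain score at 5-12 hours: 3.9 - 3.2 = 0.7, SD 1.4, effect size 0.7/1.4 = 0.5. A two-sided t-test at 0.05 with 90% power needs 85.03, so 86 per group; 86/(1 - 0.10) = 95.6, so 96 per group and 192 in all. This reproduces. It does not concern MME, for which the documents give no mean, SD or target difference. Only the 86 per arm is carried forward.

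**Direct arithmetic (discharged scored 0, identical use in both arms).** False shift in the floor window = (difference in day-0 share) x (mean first-night MME). At an assumed 10-point gap this is 0.10 x 5 = 0.5 MME to 0.10 x 20 = 2.0 MME. The home window shifts by the same amount in the opposite direction, and the sum by 0.

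**Simulated false-positive rates.** Every input except the 86 per arm is assumed: log-normal opioid need (CV 0.8, extra log-SD 0.4 per component); first-night mean 5, 10 or 20 MME; 0, 30 or 50% non-users that night; other home use mean 30 MME; later floor hours as one window; 2,000 runs per setting. The 10-point gaps are 30 v 40, 45 v 55 and 60 v 70% day-0 discharge, giving 3 x 3 x 3 = 27 settings.

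| Analysis, no true effect | Day-0 gap | t-test | Mann-Whitney |
|---|---|---|---|
| Later floor, scored 0 | 10 points | 7-16% | 10-27% |
| Later floor, scored 0 | 5 points (30 v 35%) | 5-7% | 6-9% |
| Later floor, not observed | 10 points | 4-6% | 4-6% |

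Across both tests, the scored-0 rate with equal discharge (35 v 35%) is 4-6%. At a 10-point gap the home window gives 4-8% and the cumulative total 4-6%. A model that kept a separate 8-hour window gave, at a 10-point gap, 10-15% (t-test) and 13-25% (Mann-Whitney) scored 0, 4-7% not observed, and 3-6% for the total.

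**Selection under the not-observed rule.** If low-need patients leave earlier (assumed correlation 0.5, 30% non-users, 10-point gap), the false difference, 6 minus 15 mmHg, is +0.2 to +1.8 MME, with rejection in 5-7% of runs.

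**Power (t-test, 35% day-0 discharge in both arms, 0 or 30% non-users).**

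| True effect | Cumulative total | Later floor, inpatients only |
|---|---|---|
| 40% cut, first night only | 7-25% | 49-82% |
| 40% first night, 20% at home | 46-68% | 52-82% |
| 40% cut all week | 93-97% | 52-82% |

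The total is weak in the first row because home use dominates it: 30/50 = 60% to 30/35 = 86% of the modelled total.

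**Visit timing.** The 1-week visit is generally on day 5-7 but may slip by about a week, with no strict window (Section 2.3). If use decays with half-life h days, recording to day 14 instead of day 7 multiplies it by (1 - 2^(-14/h))/(1 - 2^(-7/h)) = 1.01, 1.09 and 1.20 for h = 1, 2 and 3.

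**The case against.** The strongest reply is that the plan, read naturally, does not score discharged patients 0. Section 2.3 ties the timed windows to the hospital stay, so a patient who has left is not observed, and the error rate is then close to nominal. The selection that remains pushes against 6 mmHg when low-need patients leave first, so it cannot manufacture a benefit for that arm. This stands, and it makes selection, not false positives, the main point.

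The 10-point gap is Aim #4's threshold for clinical importance, not an expected difference. Less pain is also one of the routes by which stay is expected to shorten, so a gap with identical opioid need has to come from the other routes. Both points stand. So does the point that the appendix forms are not in the available text and may hold a scoring rule. The objection that the model merges the floor windows does not: keeping an 8-hour window separate gives similar rates.

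Three stronger readings are tempting but unsupported:

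- A reader might infer that Aim 1 as planned carries a 10-27% false-positive rate. That needs the scoring rule which Section 2.3 supports least, and an assumed gap.
- A reader might infer that the total should replace the windows, or must be significant before a window difference is believed. With a real 40% first-night cut and 45 v 35% day-0 discharge (0 or 30% non-users), the inpatient-only t-test was significant in 46-78% of runs, but both it and the total in only 5-24%. Such a rule would block most true first-night effects.
- A reader might infer that MME after floor hour 20 is not collected. Section 2.3 suggests that it may be; what is missing is an analysis window, and the amount involved is unknown.

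**Conclusion.** The point holds as a cheap improvement. That Aim 1 lacks a per-patient total, and that discharge decides where first-night opioids are counted, follows from the wording and can be stated with high confidence. The consequence is less certain. With discharged patients not observed, the later floor windows keep about a 5% error rate but describe patients still in hospital, not the randomised groups. Inflated error arises only with 0-scoring and a between-arm difference in day-0 discharge, and its size rests wholly on assumed MME levels and discharge shares. The PACU window is untouched by discharge home, and the home window is little affected. If day-0 discharge is similar between arms, the problem is small. Neither the total nor the windows is the better analysis in every scenario, so both are needed.

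**What to change.** 1. Add to Aim 1 a supportive, pre-specified cumulative MME per patient: PACU, plus all floor use including after hour 20, plus home use, compared by randomised group.
2. Record the date of the 1-week visit. Either count use to a fixed postoperative day where the data allow, or end at the visit and add a sensitivity analysis by visit timing.
3. State how patients without a home pill count are handled, for example an available-data analysis plus a sensitivity analysis. Section 2.3 keeps non-returners in the final dataset, but their total cannot be computed without a rule.
4. Treat MME in floor windows after discharge as not observed rather than 0, and show the number still in hospital by arm.
5. Keep the window comparisons. Report later-floor differences beside the discharge proportions and the cumulative total, noting that they are conditional on still being in hospital. Do not require the total to be significant.
6. Optional: for day-0 patients "the CRC will call the following morning to evaluate pain" already; ask then how many opioid pills were taken since discharge, so that first-night use can be compared wherever it was taken.

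The cost is SAP wording, one more analysis and, if the form lacks it, a visit date. Inpatient MME and home pill counts are already planned, and no visit is added. The downside is the total's low power for a first-night-only effect, which is why the windows stay. The optional question sets self-report at home against chart data in hospital, and needs recall to Monday after Friday surgery.

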Similar to aim 1, postoperative pain scores will be assessed at following time points: during the PACU stay, during the first 4 hours on the floor, next 8 hours, and the following 8 hours, as well as the final scores immediately prior to discharge (or via phone call if discharged same-day). There will be only one measurement of pain at each bodily location during the PACU stay, as well as at discharge. However, the average and maximum postoperative pain scores will be calculated for each of the time intervals (the first 4 hours on the floor, next 8 hours, and the following 8 hours). The comparison of average and maximum scores at each time point between the two groups will be performed using independent sample t-test or Mann-Whitney U test, as appropriate.

The association between patient demographic or clinical characteristics and differences in medication use or pain scores will be assessed using multivariate regression. The appropriate type of regression (logistic or linear) used will be determined after data collection is complete.

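### Separate tests at each interval give no estimate of the pain effect across the stay, no test of whether it changes with time, and rest on whoever is still observed

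*Combined protocol and SAP*

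**What the plan says.** Aim 2 (Combined protocol and SAP, sections 1.2 and 2.4) compares average and maximum pain between arms "over time at pre-specified time intervals through discharge". Section 1.2 lists the intervals: PACU, the first 4 hours on the floor, the next 8, the following 8, and a final score.

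On collection, the text with Table 2 in section 2.3 says "we will record scores every 2 hours during the inpatient stay while the patient is awake". Table 2 schedules 3 + 4 + 4 = 11 floor scores per location, plus one PACU score and one final score. Section 2.4 reduces the floor scores to patient-level summaries: "the average and maximum postoperative pain scores will be calculated for each of the time intervals".

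The between-arm analysis is "The comparison of average and maximum scores at each time point between the two groups will be performed using independent sample t-test", or a Mann-Whitney test. The only other analysis of pain is a regression on patient characteristics: "The association between patient demographic or clinical characteristics and differences in medication use or pain scores will be assessed using multivariate regression". Its form is left open: "The appropriate type of regression (logistic or linear) used will be determined after data collection is complete".

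On missing scores, section 2.3 accepts that "there is the potential for missing data in the first 24-hour period", because same-day or next-day discharge is the target. No missing rate and no method for handling missing scores is given.

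**The concern.** Three things follow from testing each interval on its own.

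- **No overall effect.** Nothing in section 2.4 combines the intervals into one arm effect over the stay. There is no mixed model, GEE, repeated-measures ANOVA, area under the curve or other whole-period summary.
- **No test of time dependence.** If one interval reaches p < 0.05 and its neighbour does not, the plan has no analysis that says whether the two effects differ. The point has practical weight because section 2.4 reports the feasibility result as specific to hours 5-12 and sizes the trial on it.
- **Changing patient sets.** Inpatient scores stop at discharge and are not taken during sleep. A patient discharged the same day gives one score by phone the next morning, which Table 2 counts as the final score and not as an interval score. If pressure affects pain, and pain affects discharge or sleep, the patients left in a later interval are no longer the groups that were randomised.

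At stake are what the trial can say about pain beyond single intervals, and how far the later-interval comparisons can be trusted.

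**Working it through.** **Inputs.** From section 2.4: "The average score in the 6 mmHg group was 3.2, and that in 15 mmHg historical group was 3.9" (hours 5-12), SD 1.4, significance level 0.05, power 90%, 86 per arm, inflation for 10% ineligible. Not in the documents, so assumed: the between-interval correlation ρ (0.4 to 0.7, with 0.9 as an unfavourable case) and the share of scores missing.

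**1. The plan's own figure.** Effect size = (3.9 − 3.2)/1.4 = 0.5. The two-sided t-test solution for 90% power is 85.03, so 86 per arm and 172 in total; power at 86 is 90.3%. 172/0.9 = 191.1, so 192. The figure reproduces. It covers one cross-sectional comparison with everyone observed.

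**2. That comparison with incomplete scores.** If 80%, 60% or 50% of the 86 per arm have a score at hours 5-12 (assumed), the t-test has 82.9%, 71.1% or 63.0% power, before any bias from selection.

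**3. The effect averaged over three floor intervals.** With equal SDs and complete data, the variance of a patient's mean over three intervals, relative to one interval, is (1 + 2ρ)/3. Two-sided t-test power at 86 per arm:

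| ρ | (1 + 2ρ)/3 | 0.7 in all three | 0.5 in all three | 0.7 in one only (mean 0.7/3 = 0.23) |
|---|---|---|---|---|
| one interval alone | 1 | 90% | 64% | 90% if that interval is tested |
| 0.4 | 0.60 | 98.8% | 85% | 29% |
| 0.5 | 0.67 | 97.9% | 81% | 27% |
| 0.6 | 0.73 | 96.8% | 78% | 24% |
| 0.7 | 0.80 | 95.4% | 74% | 23% |
| 0.9 | 0.93 | 92% | 67% | 20% |

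The average gains when the effect is sustained and loses heavily when it is confined to one interval. It cannot replace the 5-12 hour contrast.

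**4. The arm-by-interval contrast.** The difference between two intervals within a patient has variance 2 × 1.4² × (1 − ρ). For arm effects that differ by 0.7 between two intervals, power at 86 per arm is about 79%, 90% and 99% at ρ = 0.3, 0.5 and 0.7. The trial is large enough for this test to be informative with complete data.

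**5. Selection.** Let Y1 be the earlier interval and Y2 the later one, normal with equal SDs and correlation ρ, and let missingness of Y2 depend only on Y1. Then

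mean of observed Y2 = mean of Y2 + ρ × (mean of Y1 among those observed − mean of Y1).

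If patients with less pain are likelier to be missing, both observed means move up, and the mean of the arm with less pain moves up more. The difference between arms therefore shrinks. In simulation, with a true difference of 0.7 and about 30% of later scores missing, the separate comparison showed about 0.62 to 0.66. For instance, with the log odds of a missing score falling by 1 per SD of earlier pain, it showed 0.66 at ρ = 0.4 and 0.63 at ρ = 0.7. The loss is 0.04 to 0.08, or 6% to 11% of 0.7 (0.04/0.7 and 0.08/0.7). A likelihood-based analysis using the earlier score recovered about 0.70. A steeper dependence on earlier pain increases the loss.

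**The case against.** The strongest reply is that the aim, read in full, is answered. It speaks of pre-specified intervals, section 1.2 lists them, and section 2.4 compares the arms at each. Aim 1 uses the same wording and is also analysed interval by interval. A reader might infer that the question about pain over time is never tested; the documents do not support that. Nor do they support the inference that repeated scores go unused, since the 2-hourly scores are combined into an average and a maximum within each floor interval. Only information across intervals is unused.

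It is also fair to say that:

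- the plan nowhere announces that it will read differing p-values as a time pattern, so that is a risk and not a stated intention;
- the power gain belongs to a stay-averaged effect that the protocol does not define;
- the documents give no time course for the benefit, and the one earlier result they report concerns hours 5-12;
- section 2.2 calls pain scores a secondary outcome.

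A mixed model has limits too. It extrapolates beyond discharge under a missing-at-random assumption, and if missingness depends on unrecorded pain it is biased as well. A model of the floor averages leaves out PACU, final and maximum scores, all of which Aim 2 includes.

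These points stand, and they are reasons to keep the planned tests alongside the model. They do not supply an overall effect, a test of time dependence or an answer to the changing patient sets.

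**Conclusion.** The point holds in a limited form. The per-interval tests address the aim on its interval-by-interval reading. They cannot support a statement about pain over the whole stay or about differences between intervals, and their later comparisons may rest on selected patients.

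Selection is the weightier reason to act. Its illustrated size, 0.62 to 0.66 in place of 0.7, assumes about 30% missing with dependence on earlier pain; the documents give no rate.

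The precision argument is secondary. For a sustained difference of 0.5, power rises from 64% to 74-85%, but only with an equal effect and SD in every interval, complete data and a correlation of 0.4 to 0.7. At 0.9 it is 67%, and an effect of 0.7 confined to one interval has only 23-29% power on the average (correlation 0.4 to 0.7). A reader might infer that the trial is too small. It is not shown to be: 86 per arm is correct for the comparison it was calculated for, and N does not change.

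**What to change.** For average pain, pre-specify one linear mixed model for repeated measures in section 2.4. The outcome is the average score in each floor interval (0-4, 5-12 and 13-20 hours). The terms are arm, interval and arm-by-interval, with unstructured within-patient covariance, fitted to all observed intervals. State which pain location or locations enter the model. Report:

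- (a) the 5-12 hour contrast, on which the trial was sized, as the main contrast;
- (b) the arm effect averaged over the three floor intervals;
- (c) the arm-by-interval test, before any claim that the effect depends on time.

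Keep the planned per-interval tests as supportive, including PACU, final and maximum scores and the Mann-Whitney option. State that the model treats scores absent after discharge or during sleep as missing at random given the observed scores, and report the number of patients observed per arm in each interval.

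The cost is SAP wording and one PROC MIXED model in the SAS software already named, on data already being collected. The downsides are a slightly more complex analysis and the missing-at-random assumption.
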